1.0 PURPOSE

This protocol describes the comparison of the clinical performance of the original ABCA-GIRMS (Automated Breath Carbon Analyzer – Gas Isotope Ratio Mass Spectrometer) and new ABCA2-GIRMS systems when used to analyze ratios of $^{13}\text{CO}_2$ to $^{12}\text{CO}_2$ in breath samples collected using Cairn's ^{13}C -Spirulina GEBT, that are used to calculate $^{13}\text{CO}_2$ excretion rates (kPCD min^{-1}) that describe gastric emptying rates.

[figure not shown]
2.0 BACKGROUND

The performance characteristics of the ABCA GIRMS instrument currently in use for analyzing carbon stable isotope ratios of CO_2 in breath samples collected during administration of the GEBT were established and documented in PRO-QC-114.01, Analytical Performance of ABCA GIRMS Instruments, and the associated report (submitted as part of PMA P110015).

This protocol includes studies that seek to confirm the acceptable level of clinical performance measures of the ABCA2 GIRMS system and demonstrate comparable performance characteristics to the original ABCA GIRMS system. This study will be performed in accordance with CLSI Guidance EP12-A2, User Protocol or Evaluation of Qualitative Test Performance; Approved Guideline, Second Edition and Assay Migration Studies for In Vitro Diagnostic Devices – Guidance for Industry and FDA Staff.

3.0 RESPONSIBILITIES

| Requirement | Responsibility |
|---------------------|--|
| Protocol generation | Director of Quality Assurance and Regulatory Compliance |
| Protocol approval | Clinical Laboratory Director, Chief Information and Instrumentation Officer, Director of Laboratory Operations |
| Protocol execution | Clinical Laboratory personnel |
| Data analysis | Data Management Associate, Director of Laboratory Operations, Director of Quality Assurance and Regulatory Compliance, Chief Information and Instrumentation Officer |
| Report generation | Director of Quality Assurance and Regulatory Compliance |

| Originator: | NAME (Print) | SIGNATURE | DATE |
|--------------|--------------------|--|-----------|
| Originator: | [name] |  | 9-2-2020 |
| Approved By: | [name] |  | 9/1/20 |
| Approved By: | [name] |  | 9/1/2020 |
| Approved By: | See Attached | | cc 9-3-20 |

Effective Date:**1.0 PURPOSE**

This protocol describes the comparison of the clinical performance of the original ABCA-GIRMS (Automated Breath Carbon Analyzer – Gas Isotope Ratio Mass Spectrometer) and new ABCA2-GIRMS systems when used to analyze ratios of $^{13}\text{CO}_2$ to $^{12}\text{CO}_2$ in breath samples collected using Cairn's ^{13}C -Spirulina GEBT, that are used to calculate $^{13}\text{CO}_2$ excretion rates (kPCD min^{-1}) that describe gastric emptying rates.

2.0 BACKGROUND

The performance characteristics of the ABCA GIRMS instrument currently in use for analyzing carbon stable isotope ratios of CO_2 in breath samples collected during administration of the GEBT were established and documented in PRO-QC-114.01, Analytical Performance of ABCA GIRMS Instruments, and the associated report (submitted as part of PMA P110015).

This protocol includes studies that seek to confirm the acceptable level of clinical performance measures of the ABCA2 GIRMS system and demonstrate comparable performance characteristics to the original ABCA GIRMS system. This study will be performed in accordance with CLSI Guidance EP12-A2, User Protocol or Evaluation of Qualitative Test Performance; Approved Guideline, Second Edition and Assay Migration Studies for In Vitro Diagnostic Devices – Guidance for Industry and FDA Staff.

4.0 DEFINITIONS

| Term or Abbreviation | Definition |
|--|---|
| ABCA GIRMS or ABCA2 GIRMS | Sercon's Automated Breath Carbon Analyzer Gas Isotope Ratio Mass Spectrometer, used to analyze stable isotopes of carbon in breath samples |
| Delta values ($\delta^{13}\text{C}$) | Amount of ^{13}C in a sample expressed as a ratio of carbon-13 to carbon-12: $\delta^{13}\text{C}(\text{‰}) = \frac{R_B - R_S}{R_S} * 1000$ 
Where R_B is the ratio of $^{13}\text{C}/^{12}\text{C}$ of the sample and R_S is the ratio of $^{13}\text{C}/^{12}\text{C}$ in Pee Dee Belemnite (PDB), the reference standard for these measurements.
 |
| DOB | Delta Over Baseline i.e. the difference in two delta values |
| GEBT | Gastric Emptying Breath Test |
| kPCD | 1000 x Percent Dose (of Carbon-13) Excreted, $^{13}\text{CO}_2$ excretion rate (min^{-1}) primary GEBT metric |
| Measurand | Quantity intended to be measured |
| NCR | Nonconformance Report |
| SOP | Standard Operating Procedure |
| QA | Quality Assurance |
| QC | Quality Control |

5.0 TRAINING REQUIREMENTS

Operators conducting this validation must be qualified according to the position requirements and must be successfully trained in the validation protocol and all analytical method SOPs/documentation associated with execution of this protocol. Training shall be documented, and training records maintained in accordance with Cairn's requirements stated in SOP-QA-007, Training System.

6.0 EQUIPMENT/MATERIALS

A list of equipment and materials required for execution of this protocol is provided in Table 1.

Table 1. Equipment/Materials List

| Equipment/Materials Description | Manufacturer/Vendor | Model Number/Comments | SPEC Numbers |
|---------------------------------|---------------------|-----------------------|--------------|
| ABCA GIRMS | Europa Scientific | ABCA-A | N/A |
| ABCA2 GIRMS | Sercon Limited | ABCA-C/ABCA-D | N/A |

| Equipment/Materials Description | Manufacturer/Vendor | Model Number/Comments | SPEC Numbers |
|--|------------------------|-----------------------|--------------|
| Monoject Tubes | Covidien/McKesson | 8881301710/48992 | SPEC-QA-016 |
| BD 10mL Syringes with BD 20G1 PrecisionGlide Needles | BD Diagnostics Systems | 309604 | N/A |

Information regarding test materials and reference materials will be recorded at the time of testing and documented in the validation report.

7.0 PROCEDURES

7.1 Validation Requirements: Clinical Diagnostic Agreement

Determine clinical performance characteristics for ABCA2 GIRMS according to CLSI Guideline EP12 and FDA's Guidance Assay Migration Studies for In Vitro Diagnostics by analyzing 75 sets of patient breath samples on Cairn's original ABCA GIRMS and new ABCA2 GIRMS instruments.

PRO-CD-044, ABCA2 GIRMS Clinical Performance Study - Patient Sample Collection, describes the collection of patient samples for the clinical performance studies under an IRB approved protocol. Analyze breath samples collected prior to and after consumption of the GEBT test meal according to this protocol. Analyze each set of breath samples from each participant on Cairn's original ABCA GIRMS instrument and two new ABCA2 GIRMS instruments.

Determine clinical performance by comparing the diagnosis determined by kPCD values at each individual timepoint and overall diagnosis algorithm (e.g. two out of three kPCD values below the reference range cutoff point at 90, 120, and 150 minutes or T_{max} at 240 minutes) on the original ABCA GIRMS with diagnoses determined in the same way on the new ABCA2 GIRMS instruments.

Table 2. Clinical Performance Acceptance Criteria

| Description | Justification |
|--|---|
| ABCA GIRMS instruments will be considered equivalent if: 
 ≥95% of individual diagnoses at each timepoint (45, 90, 120, 150, 180, and 240 minutes) are in agreement, and ≥95% of overall diagnosis (by algorithm) are in agreement. | A requirement for 95% diagnostic agreement allows for the few cases where a borderline subject may fall on either side of the diagnostic 'line' (reference range COP) without significant error in the DOB. |

For justification of these acceptance criteria see REP-QC-018, Validation Criteria for ABCA-GIRMS systems

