4.0 STUDY GOALS AND OBJECTIVES

The purpose of this study is to collect human breath samples for use in a validation study intended to demonstrate equivalent clinical performance of new ABCA2 GIRMS instruments to the current FDA-approved ABCA GIRMS system. The clinical performance data will be used as part of a supplement submission to FDA demonstrating that both ABCA2 GIRMS systems are suitable for use with GEBT and that the safety and efficacy of GEBT is not affected.

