5.0 SUBJECT SELECTION

Cairn personnel and their family and friends may volunteer to be a participant in this study.

Participants may also be recruited from clinical trial sites that have a population that is known to have a history of possible gastric emptying issues (intended use population for GEBT).

This study requires a minimum of seventy-five (75) and up to one hundred and twenty (120) participants.

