8.0 STATISTICAL ANALYSIS

8.1 Clinical Diagnostic Agreement

8.1.1 Determine the diagnosis at individual time points for each subject on each instrument as follows:

- Positive for gastroparesis: kPCD below the reference range cut-off point (Table 4) for the applicable time point
- Negative for gastroparesis: kPCD above the reference range cut-off point (Table 4) for the applicable time point

Table 4. Reference Range Cut-Off Points for ¹³C-Spirulina GEBT

| Timepoint | 45 min | 90 min | 120 min | 150 min | 180 min | 240 min |
|---|--------|--------|---------|---------|---------|---------|
| Reference Range COP (kPCD min ⁻¹) | 12.9 | 26.9 | 34.4 | 39.5 | 43.0 | 35.0 |

8.1.2 Determine an overall diagnosis for each subject on each instrument using the following algorithm:

- Positive for gastroparesis if two out of three of the 90-, 120-, 150-timepoints are below the reference range cutoff point (Table 4) OR T_{max} (maximum kPCD value) occurs at the 240-minute timepoint.

Note: this algorithm is not an FDA approved algorithm for determining diagnosis by GEBT but is a convenient means of consistently determining an overall diagnosis that is supported by the interpretative guidelines published in the FDA approved labeling.

8.1.3 Determine the percent agreement in diagnosis between the comparative method (original ABCA-GIRMS) and the candidate method (new ABCA2-GIRMS) at each time point and for the overall diagnosis according to CLSI Guideline EP12-A2:

Prepare a contingency table (see Table 5) showing agreement between diagnoses between the comparative and candidate methods and each time point and for the overall diagnosis.

Table 5. Example contingency table for calculating percent agreement

| Candidate Method | Comparative Method | | |
|------------------|--------------------|----------|-------|
| | Positive | Negative | Total |
| Positive | a | b | a+b |
| Negative | c | d | c+d |
| Total | a+c | b+d | n |

Calculate overall percent agreement, percent positive agreement and percent negative agreement as follows:

- Overall percent agreement = $100 \times (a+d)/n$
- Percent positive agreement = $100 \times a/(a+c)$
- Percent negative agreement = $100 \times d/(b+d)$

8.1.4 Determine the 95% confidence intervals for the agreement measures according to CLSI Guideline EP12-A2 section 10.2.2.

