8.0 STATISTICAL ANALYSIS

8.1 Bias Comparison

Compare bias in patient samples according to EP09c – Third Edition Measurement Procedure Comparison Bias Estimation Using Patient Samples.

- Calculate the difference in DOBs, between the candidate method (ABCA-C or ABCA-D) to the comparative method (ABCA-A).
- Calculate the mean difference and the standard error (calculated by dividing the standard deviation by the square root of the number of samples) of the difference.
- Calculate the 95% confidence interval and compare results to the acceptable limit of $\pm 0.5\%$ DOBs. If the interval is within this acceptance limit the results are deemed acceptable.

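### Exhibit B declares the instruments equivalent on observed agreement of at least 95%; the barest pass at 75 sets has a lower 95% limit of about 89%, and the interval computed in 8.1.4 plays no part in the conclusion.

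*Combined protocol and SAP*

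**What the plan says.** The protocol's section 4.0 sets the aim: to "demonstrate equivalent clinical performance of new ABCA2 GIRMS instruments" relative to the approved system, with the results going to FDA in a supplement.

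Exhibit B 7.1 bases this on "analyzing 75 sets of patient breath samples"; the protocol's section 5.0 allows between 75 and 120 participants. Table 2 in the same section gives the decision rule. It begins "ABCA GIRMS instruments will be considered equivalent if" and lists two conditions. The first sets a 95% threshold separately for the diagnosis at each of the six sampling times. The second is "≥95% of overall diagnosis (by algorithm) are in agreement". Both conditions are on the observed percentage. The reason printed beside them is that a few borderline subjects may fall on either side of a cut-off without much DOB error. Further justification is left to REP-QC-018, which is not among the documents.

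Exhibit B 8.1.3 defines overall agreement as 100 × (a+d)/n, and 8.1.4 adds: "Determine the 95% confidence intervals for the agreement measures according to CLSI Guideline EP12-A2 section 10.2.2". No section of the protocol or exhibits says what those intervals are compared with.

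Exhibit C (PRO-QC-191) 8.1 treats the mean DOB difference otherwise. It computes a 95% interval, sets it against the bias limit, and states: "If the interval is within this acceptance limit the results are deemed acceptable".

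**The concern.** An equivalence conclusion normally rests on what the data rule out. Table 2 rests it on the point estimate. An observed 96% in 75 sets is compatible with true agreement several points below 95%, and the interval that would show this is calculated and then left out of the decision.

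The plan already uses the interval as the test for bias in Exhibit C. The criterion that carries the word equivalent is therefore held to a weaker standard of evidence than the bias criterion applied to the same samples. What is at stake is how the result is stated in the submission: a barely passing endpoint supports agreement of roughly 89% or better, not 95% or better.

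**Working it through.** **Inputs.** n = 75 sets (Exhibit B 7.1), or 75 to 120 (protocol 5.0). Pass if observed agreement is at least 95% (Table 2). Interval level 95% (8.1.4), taken as two-sided. The EP12-A2 formula is not printed, so several methods are shown. The plan gives no power, assumed true agreement or null value for the 75, so that number cannot be reproduced.

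**Lowest passing result.** 0.95 × 75 = 71.25, so 72 agreements are needed. 71/75 = 94.7% fails and 72/75 = 96.0% passes.

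**Wilson interval for 72/75.** With p = 0.96, z = 1.960 and z² = 3.841, the limits are [p + z²/(2n) ± z·√(p(1−p)/n + z²/(4n²))] / (1 + z²/n).

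- p + z²/(2n) = 0.96 + 0.0256 = 0.9856
- z·√(0.000512 + 0.000171) = 1.960 × 0.02613 = 0.0512
- 1 + z²/n = 1.0512
- Lower limit (0.9856 − 0.0512)/1.0512 = 88.9%; upper limit (0.9856 + 0.0512)/1.0512 = 98.6%

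**Other methods, lower limit for 72/75.** Clopper-Pearson 88.8%; Wilson with continuity correction 88.0%; Wald 0.96 − 1.960 × √(0.96 × 0.04/75) = 91.6%. One-sided 95% limits are 90.4% (Wilson) and 90.0% (Clopper-Pearson). All are below 95%.

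**Other results (Wilson).**

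| Result | Observed | Lower 95% limit |
|---|---|---|
| 73/75 | 97.3% | 90.8% |
| 74/75 | 98.7% | 92.8% |
| 75/75 | 100% | 95.1% |
| 76/80 (weakest pass for n from 75 to 120) | 95.0% | 87.8% |
| 95/100 | 95.0% | 88.8% |
| 114/120 | 95.0% | 89.5% |
| 118/120 | 98.3% | 94.1% |
| 119/120 | 99.2% | 95.4% |

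With score or exact limits, a lower limit of 95% therefore needs 75/75 at 75 sets and at least 119/120 at 120 sets. Wald limits would be more generous: 74/75 gives 0.9867 − 1.960 × √(0.9867 × 0.0133/75) = 96.1%.

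**Chance that one endpoint on one instrument passes.** At 75 sets this is P(X ≤ 3), where X is the number of disagreements, binomial with n = 75. At true agreement 93% the terms for X = 0, 1, 2, 3 are 0.0043 + 0.0244 + 0.0680 + 0.1246 = 0.221.

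| True agreement | 75 sets (≥72) | 120 sets (≥114) |
|---|---|---|
| 90% | 5% | 4% |
| 92% | 14% | 15% |
| 93% | 22% | 26% |
| 95% | 48% | 61% |
| 97% | 81% | 93% |
| 99% | 99% | >99% |

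**Joint rule.** Seven endpoints must pass. If they were independent (they are not; this is illustrative), the chance of passing all seven at 75 sets would be 0.480⁷ = 0.6% when every endpoint is at 95%, 0.812⁷ = 23% at 97% and 0.936⁷ = 63% at 98%. If one timepoint alone is poor and the other six are near-perfect, the chance of an overall pass is close to the single-endpoint figure.

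**The case against.** **The rule is strict taken as a whole.** Seven endpoints must pass together, and an instrument at a true 95% fails any one of them slightly more often than it passes. One poor timepoint is already rejected 86% of the time at 92% and 95% of the time at 90%. If both ABCA2 instruments must pass, the chance at 92% is at most 14%, and about 2% (0.14²) if they were independent. This stands. The exposure is to a single timepoint a few points below 95%, not to general leniency.

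**The 95% is a tolerance for borderline subjects, and DOB error is tested separately.** Exhibit C checks mean bias, bias at six DOB values and total analytical error on the same samples, so it complements Table 2 as well as contrasting with it. A mean DOB difference is also a different quantity from a binary classification. This explains why some disagreement is acceptable. It does not say how much true agreement the data have shown. REP-QC-018 may defend the choice of 95%, but nothing in the supplied text gives the interval a role.

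**No claim of 95% true agreement is written down.** A reader might infer that the sponsor will report true agreement of 95% as demonstrated. The documents do not say so. Table 2 concerns observed diagnoses, protocol section 14.0 speaks of comparable performance, and the 8.1.4 intervals would be available when the report is written. The point is narrower: the word equivalent is earned without reference to those intervals.

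**Conclusion.** The point holds in a limited form. Table 2 lets observed agreement alone decide equivalence. For one comparison at 75 sets, a bare pass supports agreement of about 89% or better (88.0% to 91.6% over the two-sided methods tried). Over the permitted 75 to 120 sets, the weakest pass gives 87.8% by Wilson. One timepoint at a true 93% passes about 22% of the time at 75 sets.

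This rests on three assumptions: a two-sided 95% interval, a Wilson or similar formula, and separate analysis of ABCA-C and ABCA-D, which the plan does not specify. Pooling the two instruments, with 150 results treated as independent, would make the lowest pass 143/150, with a Wilson lower limit of 90.7%; that is still below 95%.

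The single-endpoint pass rates should not be read as the chance that a poor instrument passes the whole study. That chance is much lower when several endpoints are poor. Nor do the figures make the 95% goal unworkable: at true agreement of 99%, one endpoint passes 99% of the time.

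**What to change.** In Exhibit B Table 2, keep observed agreement of at least 95% at every endpoint as the pass rule, with the same number of participants. Change the opening words from *will be considered equivalent if* to *meet the minimum performance goal if*.

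Add a statement to Table 2 and to the report that the agreement demonstrated is the lower 95% limit from 8.1.4, given for each endpoint and each ABCA2 instrument. For example, 72/75 would be reported as 96.0% observed, lower 95% limit 88.9% if the Wilson method is used. Describe agreement of 95% or more as demonstrated only where that limit reaches 95%. Print the interval formula in 8.1.4, so that the figure does not depend on a later choice of method.

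The cost is wording only; 8.1.4 already calls for the intervals. The downside is a less favourable stated figure: roughly 88% to 95% for results near the threshold, in place of a bare statement that the 95% rule was met.

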7.2 General Procedures

- 7.2.1 Accession and analyze breath samples according to SOP-CD-021, GEBT Breath Sample Accessioning and Chain of Custody and SOP-CD-005, Breath Test Processing.
- 7.2.2 Prepare QC standards and reference gases for this protocol according to SOP-QC-043, QC Gas Preparation for ABCA GIRMS.
- 7.2.3 Run the ABCA GIRMS and ABCA2 GIRMS systems according to SOP-QC-017, Operation, Calibration and Maintenance – ABCA GIRMS and SOP-QC-090, Operation, Calibration and Maintenance – ABCA2 GIRMS.
- 7.2.4 Analyze breath samples first on the original ABCA-GIRMS system and then on either the ABCA-C or ABCA-D ABCA2 GIRMS system. Analyze samples a third time on the ABCA2 GIRMS system on which the samples have not yet been analyzed. Note: the original ABCA-GIRMS system, ABCA-A utilizes a larger sample of breath (~4 mL) than the ABCA2-GIRMS systems (1-2 mL). For this reason, all samples will be analyzed on ABCA-A first. The order in which samples are analyzed on ABCA-C and ABCA-D will be randomized to minimize any bias cause by running the same samples on different instruments in the same order as outlined in Table 3.

Table 3. Randomization Table

| Subject Number | Study Participant Breath Sample Analysis Order | | |
|----------------|--|--------------------|--------------------|
| | ABCA GIRMS (A) | ABCA2 GIRMS (C) | ABCA2 GIRMS (D) |
| 001 | 1 | 2 | 3 |
| 002 | 1 | 3 | 2 |
| 003 | 1 | 3 | 2 |
| 004 | 1 | 2 | 3 |
| Etc | Etc | Etc | Etc |

- 7.2.5 Enter LAF, gas standards and subject breath sample delta values into the Linearity Adjustment Excel workbook according to SOP-QC-090 for samples analyzed on the ABCA2 GIRMS systems.
- 7.2.6 Enter Quality Control standards data on the appropriate QC charts which are located in the instrument laboratory. Verify that QC values are within accepted ranges according to SOP-QC-090. If QC data is outside the accepted ranges, initiate a nonconformance report (NCR) according to SOP-QA-014, Control and Handling of Nonconformances, to investigate a potential cause of the nonconformance.
- 7.2.7 Enter DOB and kPCD results for each patient on each instrument into a spreadsheet for analysis.

8.0 STATISTICAL ANALYSIS

8.1 Clinical Diagnostic Agreement

8.1.1 Determine the diagnosis at individual time points for each subject on each instrument as follows:

- Positive for gastroparesis: kPCD below the reference range cut-off point (Table 4) for the applicable time point
- Negative for gastroparesis: kPCD above the reference range cut-off point (Table 4) for the applicable time point

Table 4. Reference Range Cut-Off Points for ¹³C-Spirulina GEBT

| Timepoint | 45 min | 90 min | 120 min | 150 min | 180 min | 240 min |
|---|--------|--------|---------|---------|---------|---------|
| Reference Range COP (kPCD min ⁻¹) | 12.9 | 26.9 | 34.4 | 39.5 | 43.0 | 35.0 |

8.1.2 Determine an overall diagnosis for each subject on each instrument using the following algorithm:

- Positive for gastroparesis if two out of three of the 90-, 120-, 150-timepoints are below the reference range cutoff point (Table 4) OR T_{max} (maximum kPCD value) occurs at the 240-minute timepoint.

Note: this algorithm is not an FDA approved algorithm for determining diagnosis by GEBT but is a convenient means of consistently determining an overall diagnosis that is supported by the interpretative guidelines published in the FDA approved labeling.

8.1.3 Determine the percent agreement in diagnosis between the comparative method (original ABCA-GIRMS) and the candidate method (new ABCA2-GIRMS) at each time point and for the overall diagnosis according to CLSI Guideline EP12-A2:

Prepare a contingency table (see Table 5) showing agreement between diagnoses between the comparative and candidate methods and each time point and for the overall diagnosis.

Table 5. Example contingency table for calculating percent agreement

| Candidate Method | Comparative Method | | |
|------------------|--------------------|----------|-------|
| | Positive | Negative | Total |
| Positive | a | b | a+b |
| Negative | c | d | c+d |
| Total | a+c | b+d | n |

Calculate overall percent agreement, percent positive agreement and percent negative agreement as follows:

- Overall percent agreement = $100 \times (a+d)/n$
- Percent positive agreement = $100 \times a/(a+c)$
- Percent negative agreement = $100 \times d/(b+d)$

8.1.4 Determine the 95% confidence intervals for the agreement measures according to CLSI Guideline EP12-A2 section 10.2.2.

